# AIM 4. Monitor for resistance and response to subsequent treatment regimen among individuals who switched off CAB +RPV LA regimen

The analysis will be performed in all individuals who switched off CAB+RPV LA regimen. The ARV regimen received after discontinuation of CAB+RPV LA regimen will be described and categorised as follows: 2NRTI+PI, 2NRTI+NNRTI, 2NRTI+INsTI, and other. All regimen changes during the 48 month follow-up period will be captured and summarized.

The proportion of participants with HIV RNA <50 copies/mL at 12, 24, 36 and 48 months after discontinuation of CAB+RPV LA regimen will be estimated by the number of participants with HIV RNA <50 copies/mL at each time point divided by the total number of participants with discontinuation of CAB+RPV LA regimen. CD4 counts will also be assessed. The associated two-sided 95% exact (Clopper–Pearson) confidence intervals will be calculated.

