### 7. RESEARCH QUESTION AND OBJECTIVE(S)

Following the initiation of CAB+RPV LA regimen among people living with HIV (PLWH), the study will aim to assess effectiveness, discontinuation, and resistance over 24-months of follow-up period in approximately 1000 participants.

The specific objectives are to:

- 1. Describe study population initiating CAB+RPV LA regimen, by baseline demographic and clinical characteristics
- 2. Assess adherence, durability and discontinuation for PLWH starting CAB+RPV LA regimen
  - Proportion of participants discontinuing the CAB+RPV LA regimen and lost to follow-up will be assessed.
    - Reasons for discontinuation will be assessed.
  - Non adherence to dosing schedule will be assessed by
    - a. Estimating the number of participants that missed one or more consecutive injections without taking daily oral bridging therapy or any other oral ARV regimen while not on CAB+RPV LA regimen and mean and median number of injections missed during a 12-month period
    - b. Estimating the number of participants who received the injections seven or more days later than their scheduled injection visit and median duration of delayed injections
- 3. Assess the clinical effectiveness (i.e. proportion of participants experiencing virologic failure) among PLWH who initiate CAB+RPV LA regimen and had suppressed viral load (VL <50 copies/mL) at regimen initiation
  - Estimate the proportion of participants with virologic failure, during the first 6 months after initiation of CAB+RPV LA regimen
  - Estimate the proportion of participants with virologic failure at 6, 12 and 24 months after initiation of CAB+RPV LA regimen
- 4. Monitor for resistance in case of VF while on CAB+RPV LA or after switching to a subsequent ARV regimen among individuals who switched off CAB+RPV LA regimen for any reason
  - Describe the ARV regimen participants are switched to after discontinuation of CAB+RPV LA regimen
  - Describe virologic outcomes at 12, 24, 36 and 48 months after discontinuation of CAB+RPV LA regimen
  - Monitor for virologic failure and resistance during the 48 months following the switch
    - Resistance test to be done for all participants with virologic failure during the follow-up period

 HIV subtype test to be done for participants with virologic failure during the follow-up period, if subtype data is not available

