ANTDRUG	Drug Name	Category Values	1=Abacavir 2=Didanosine 3=Efavirenz 4=Lamivudine 5=Lamivudine + Zidovudine 6=Nelfinavir 7=Nevirapine 8=Ritonavir 9=Saquinavir 10=Saquinavir mesylate 11=Satvudine 12=Zalcitabine 13=Zidovudine 14=Amprenavir 15=Indinavir 16=Delavirdine mesylate 17=Lopinavir + Ritonavir 18=Abacavir + Lamivudine + Zidovudine 19=Tenofovir disoproxil fumarate 20=Adefovir dipivoxil 21=Enfuvirtide 22=Atazanavir 23=Emtricitabine 24=Fosamprenavir calcium 25=Abacavir + Lamivudine 26=Tenofovir disoproxil fumarate + Emtricitabine 27=Entecavir 28=Tipranavir 29=Efavirenz+Tenofovir disoproxil fumarate+Emtricitabine 30=Telbivudine 31=Darunavir 32=Raltegravir 33=Maraviroc 34=Etravirine 35=Rilpivirine 36=Rilpivirine+Emtricitabine+Tenofovir disoproxil fumarate 37=Elvitegravir+Cobicistat+Emtricitabine+Tenofovir disoproxil fumarate 38=Dolutegravir 39=Elvitegravir 40=Cobicistat 41=Abacavir+Dolutegravir+Lamivudine 42=Darunavir+Cobicistat 43=Atazanavir+Cobicistat 44=Lamivudine+Raltegravir 45=Elvitegravir+Cobicistat+Emtricitabine+Tenofovir alafenamide 46=Rilpivirine+Emtricitabine+Tenofovir alafenamide 47=Emtricitabine+Tenofovir disoproxil fumarate 51=Lamivudine+Tenofovir disoproxil fumarate 51=Lamivudine+Tenofovir disoproxil fumarate 55=Dolutegravir+Lamivudine+Tenofovir disoproxil fumarate 56=Dolutegravir+Lamivudine 57=Darunavir+Cobicistat+Emtricitabine+Tenofovir disoproxil fumarate 58=Fostemsavir 59=Cabotegravir 60=Rilpivirine 61=Other regimen not listed above
ANTSTREAS	Reason for Stopping	Category Values	1=Virological Failure 2=Adverse Event 3=Drug Interaction 4=Clinical Trial Enrolment 5=Patient's Decision 6=Other

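### Aim 4 reports post-switch suppression only as one pooled proportion per time point, so re-suppression among those who left CAB+RPV LA with virologic failure or resistance cannot be recovered

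*Protocol*

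**What the plan says.** Objective 4 (protocol Section 7) covers failure and resistance on CAB+RPV LA or "after switching to a subsequent ARV regimen among individuals who switched off CAB+RPV LA regimen for any reason". The Aim 4 heading in Section 8.7 adds response on the next regimen.

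The analysis under that heading has three fixed parts:

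- **Population.** "The analysis will be performed in all individuals who switched off CAB+RPV LA regimen".
- **Response.** "The proportion of participants with HIV RNA <50 copies/mL at 12, 24, 36 and 48 months after discontinuation of CAB+RPV LA regimen" is the measure, and the count at each time point is "divided by the total number of participants with discontinuation of CAB+RPV LA regimen", with exact (Clopper–Pearson) 95% intervals.
- **Regimens.** The new regimen is "described and categorised as follows: 2NRTI+PI, 2NRTI+NNRTI, 2NRTI+INsTI, and other". The section adds: "All regimen changes during the 48 month follow-up period will be captured and summarized".

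The drug list on the case report form (Annex 1, ANTDRUG) includes "56=Dolutegravir+Lamivudine". That combination contains one NRTI, so it fits none of the three two-NRTI classes and can only be counted under *other*.

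**The concern.** Table 1 in Section 8.3.2 lists very different reasons for leaving. Virological failure (1.1) and resistance (1.5) stand beside pregnancy, injection site reaction, drug supply and the individual's own wish. For someone who leaves suppressed, a later result below 50 copies/mL means suppression was maintained. For someone who leaves with failure, it means suppression was regained. A single proportion averages the two, with weights set by why people stopped. It can therefore move when the mix of reasons moves, although response within each group is unchanged.

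The protocol itself expects the failure group to differ. Section 8.4 reports that all 3 confirmed failures in the cited trial selected resistance mutations, and it assumes 50% resistance among failures here. How this group does on its next regimen is a natural question to put to an analysis of response after switching, and the specified tables do not answer it.

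**Working it through.** **1. Is the split made elsewhere in the protocol?**

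- The opening of Section 8.7 stratifies results by dosing interval and presents hepatitis B or C co-infection separately. Neither isolates failures.
- Aim 2 tabulates reasons for discontinuation and counts those with confirmed virologic failure (CVF) who stay on the regimen. It does not link reason to post-switch outcome.
- Aim 3 reports the proportion failing and, among failures, the proportion with resistance. It concerns time on CAB+RPV LA.
- The factor models that follow Aim 4 cover virologic failure, non-adherence, discontinuation and resistance. Post-switch suppression is not among the outcomes.

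The number of failures is therefore known. Their post-switch response is not.

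**2. Size of the groups (Section 8.4, N = 1000).**

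- Failures: 1000 × 0.02 = 20 to 1000 × 0.06 = 60, the protocol's own figure.
- Discontinuers: 1000 × 0.08 = 80 to 1000 × 0.16 = 160.
- Share of failures if all of them switch: 20/160 = 12.5%; 20/80 = 25%; 60/160 = 37.5%; 60/80 = 75%.

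These shares are upper bounds, because Aim 2 expects some people with CVF to stay on. The 75% also pairs the highest failure count with the lowest discontinuation count.

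**3. What the pooled figure leaves open (no assumption about response).** Let D be discontinuers, F failures among them and X suppressed. The number of failures suppressed lies between max(0, X − (D − F)) and min(F, X).

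| D | F | X (pooled) | Failures suppressed |
|---|---|---|---|
| 160 | 20 | 144 (90%) | 4 to 20 (20% to 100%) |
| 120 | 20 | 108 (90%) | 8 to 20 (40% to 100%) |
| 160 | 60 | 136 (85%) | 36 to 60 (60% to 100%) |

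**4. Illustration with assumed response.** Pooled = [(D − F)·s0 + F·sF]/D, with D = 160 and F = 20. Here s0 is suppression in the other switchers and sF is suppression in failures. Neither is given in the protocol; s0 is assumed to be 95% or 90%.

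| sF | s0 = 95% | s0 = 90% |
|---|---|---|
| 40% | 141/160 = 88.1% | 134/160 = 83.8% |
| 60% | 145/160 = 90.6% | 138/160 = 86.3% |
| 80% | 149/160 = 93.1% | 142/160 = 88.8% |
| 95% | 152/160 = 95.0% | 145/160 = 90.6% |

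The same 145/160 arises from 60% re-suppression with s0 = 95% and from 95% re-suppression with s0 = 90%. At s0 = 95%, the exact 95% intervals for sF of 40% and 95% overlap (82.1% to 92.7% and 90.4% to 97.8%).

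**5. Is a separate estimate feasible?** The exact method first reproduces Table 4 at 50% resistance: n = 20 gives 27.2% to 72.8% (width 0.456, printed 0.46) and n = 60 gives 36.8% to 63.2% (width 0.264, printed 0.26). Those are half-widths of 22.8 and 13.2 points. For suppression among failures:

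| n | At 80% | Half-width | At 60% | Half-width |
|---|---|---|---|---|
| 20 | 56.3% to 94.3% | 19.0 | 36.1% to 80.9% | 22.4 |
| 60 | 67.7% to 89.2% | 10.8 | 46.5% to 72.4% | 12.9 |

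This is no worse than the precision the protocol accepts for resistance in groups of the same size.

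**The case against.** The strongest defence is that the pooled population is what Objective 4 asks for. It covers switches for any reason, its listed outputs are descriptive, and no objective names re-suppression among failures. The study tests no hypothesis, and a statistical analysis plan that is not shown here could add the breakdown. Much of this stands. A reader might infer that Aim 4 contradicts its objective; it does not, and the pooled figure should stay. What remains is that the protocol has already written the population, denominator and regimen list, and these cannot show response where it is most in doubt.

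Other stronger readings also lack support:

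- *The failure group is hidden altogether.* Its size, the reasons for stopping and on-regimen resistance are reported under Aims 2 and 3.
- *The 48-month follow-up exists to show whether failure costs later treatment options.* The protocol does not say so. Section 8.1 ties the period to having resistance data for people who discontinue and then fail.
- *Failures will dominate the pool.* The 75% is an extreme bound. With many failures the pooled figure would also fall visibly: at D = 160, F = 60, s0 = 95% and sF = 40% it is 119/160 = 74.4%. Masking matters most when failures are few.
- *Re-use of the INSTI or NNRTI class cannot be seen.* Two of the three named categories show it overall for two-NRTI combinations, and regimen changes are summarised. What is missing is the link to failure and a place for two-drug regimens. Rebuilding the whole category list would be a matter of preference.

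**Conclusion.** The point holds as a weakness in a stated analysis. It is not a contradiction and not a gap in data capture. As specified, Aim 4 cannot show whether people who left CAB+RPV LA with virologic failure or resistance re-suppress, or on what regimen. In the clearest example, a pooled 90% (144/160, 20 failures) is compatible with 20% to 100% re-suppression among the failures.

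That range is pure arithmetic on counts within the protocol's planning ranges. It assumes that all 20 failures are among the discontinuers. The table in step 4 also rests on assumed suppression rates and only illustrates the point. That two-drug regimens fall into *other* is inferred from the category list, but no other reading fits. The change is worth making before the first post-switch results are tabulated.

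**What to change.** Amend the Aim 4 wording in Section 8.7:

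1. Keep the pooled proportion at 12, 24, 36 and 48 months.
2. Report post-switch viral load, virologic failure and resistance separately, with exact intervals, for (a) those who switched with CVF or resistance on CAB+RPV LA and (b) all other switchers. State how someone who met CVF, stayed on the regimen and left later is classified.
3. Add a two-drug category to the regimen list, so that these regimens are not merged into *other*, and cross-tabulate regimen with (a) and (b).

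No new data are needed. Discontinuation codes, viral loads, resistance results and drug names with dates are all on the case report form. The change affects reporting only, not anyone's treatment. The price is imprecision in group (a): half-widths of about 11 points (n = 60) to 19 points (n = 20) at 80% suppression, and more if some failures stay on the regimen. The split should be presented as descriptive.

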# Assessment of factors associated with non-adherence, virologic failure, discontinuation and resistance

Univariable and multivariable analyses will be performed to identify factors that probably modified the effect of the study treatment on the risk of outcomes of interest. Cox regression models will be used to assess the factors associated with virologic failure, with non-adherence and with the discontinuation of CAB+RPV LA regimen. Logistic regression will be used to assess factors associated with drug resistance among participants with virological failure, if the number of events allow this analysis. Variables with univariable P<0.20 will be retained for the multivariable analysis.

All variables described at section 8.3.3 will be assessed. We will assess whether continuous variables will be better modelled as continuous variables or as terciles based on the lowest value of Akaike's information criterion (AIC) for the corresponding univariable Cox regression models or univariable logistic regression models according to the outcome of interest, and grouped together the closest values in order to obtain two classes for certain variables.

Sensitivity Analysis: As some parameters with missing data can influence the outcome of interest, to quantify the potential effect, we will create 5 datasets in which missing data will be replaced using Rubin's multiple imputation method. Instead of filling in a single value for each missing value, multiple imputation procedure replaces each missing value with a set of plausible values that represent the uncertainty about the right value to impute. Analyses will be run on each of the 5 data sets, and the results will be combined with Rubin's rules. Pooling the multiple parameter estimates from the 5 datasets into one estimate along with its variance (which combines the conventional sampling variance and the extra variance caused by the missing data) will help understand the effect of the missing data.

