#### 8.3.3. Confounders and effect modifiers

The study will examine the effect of the following potential confounders and effect modifiers on the risk for outcomes of interest.

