#### **Demographic variables**

- Age
- Sex
- Route of HIV Infection
- Ethnic origin
- Geographic region
- Number of years since HIV diagnosis
- Date of ART initiation
- Date CAB+RPV LA started

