### 8.4. Study size

The study will aim to enroll 1000 PLWH with VL <50 copies/mL, without present or past evidence of viral resistance to, and no prior virological failure with agents of the NNRTI and INI class initiating CAB+RPV LA regimen.

There is no formal statistical hypothesis to be tested in these analyses. The study will focus on absolute effectiveness estimation. Confidence intervals, constructed using the exact Clopper-Pearson method based on the cumulative probabilities of the binomial distribution, are presented in Table 2, 3, 4 and are designed to give estimates of precision.

It is anticipated that data from 1000 participants are thought adequate to meet the study objectives. In the ATLAS study in which participants switched from their PI, NNRTI, or INSTI based oral triple therapy regimen to CAB+RPV LA regimen, the percentage of participants with virologic failure (2 confirmed HIV RNA  $\geq$ 50 copies/mL) and treatment discontinuation were, respectively, 1.6% (95% CI 0.5 to 3.4) and 8.4% (95% CI 5.6 to 12.1) at week 48. Among the 3 individuals with confirmed virological failure, all selected drug resistance mutations. For resistance, we assume a 50% resistance rate at month-24 among those with virological failure.

With 1000 individuals, the precision for the estimation of virologic failure rate will range between 0.9 and 1.5% for a failure rate ranging from 2 to 6% as shown below in Table 2.

Confidence Level	Sample Size (N)	CI Width	Virologic Failure (P)	Lower Limit	Upper Limit
0.95	1000	0.019	0.02	0.012	0.031
0.95	1000	0.023	0.03	0.020	0.043
0.95	1000	0.025	0.04	0.029	0.054
0.95	1000	0.028	0.05	0.037	0.065
0.95	1000	0.031	0.06	0.046	0.077

The corresponding precision for the discontinuation rate will range between 1.7 to 2.3 for a rate ranging from 8 to 16% as shown below in Table 3.

Confidence Level	Sample Size (N)	CI Width	Discontinuation (P)	Lower Limit	Upper Limit
0.95	1000	0.035	0.08	0.064	0.099
0.95	1000	0.038	0.10	0.082	0.120
0.95	1000	0.041	0.12	0.101	0.142
0.95	1000	0.044	0.14	0.119	0.163
0.95	1000	0.046	0.16	0.138	0.184

If the virological failure rate is ranging from 2 to 6%, then the number of participants to be tested for genotypic resistance will range from 20 to 60 individuals. With these numbers of subjects, the precision for the estimation of resistance rate will range from 12.7% (with 60 individuals) to 21.9% (with 20 individuals) for resistance rate of 50%, as shown below in table 4.

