#### 8.7. Data analysis

All enrolled participants who receive at least one dose of the CAB+RPV LA regimen will be included in the analysis. Participants who are prescribed but never receive a dose of CAB+RPV LA regimen will be excluded from the analysis. Study results will be stratified by the regimen used (Q4/Monthly dosing vs Q8/Every 2 month dosing). Further, study results for co-infected patients with hepatitis B or C will be presented separately. All continuous variables will be summarized using the following descriptive statistics: n (non-missing sample size), mean, standard deviation, 1st quartile, median, 3rd quartile, maximum and minimum. The frequency and percentages (based on the non-missing sample size) of observed levels will be reported for all categorical variables. Data will be analyzed using SAS®, SPSS® or STATA®.

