#### eForm Code: LAREG eForm Title: CAB+RPV LA regimen - Annotations Table

ID	CODE	NAME	EXP.CODE	TYPE	FMT/LEN	DERIVATION	CAT. VALUES
1	20R1ID D	Subject ID	20R1ID D	Text	10	R2F:DEMOG:20R3ID	
2	LDSTDAT	Date lead-in regimen started	LDSTDAT	Date/Time	aa/mm/yyyy		
3	LDREG	Regimen used for lead-in	LDREG	Category	11		1=CAB and RPV 2=CAB Only 3=RPV Only
4	LDADHERE	Did the subject adhere to the lead-in regimen?	LDADHERE	Category	3		N=No Y=Yes
5		If no, how many days were missed	LDDYMISS	Integer	#9		
6		receive the CAB+RPV	LDCONT	Category	3		N=No Y=Yes
7	LDREAS	If no, please give reason did not continue	LDREAS	Text	500		
8			DSCHEDDAT	Date/ Lime	da/mm/yyyy	I, Max Repeats: 20, Main Row Type: Single-Line, Sub Row Type: Multi-Line	
9	DSTYPE	Dosing Type	DSTYPE	Category	10		1=Initiation Z=1-Monthly 3=Z-Monthly
10	DSTYPECH	Change in Dosing Schedule Type	?DSTYPECH	Category	3		N=No Y=Yes
11	DSTYPEREAS	Reason for change in dosing schedule	DSTYPEREAS	Text	500		
12	DGIVEN	Was the injection given?	DGIVEN	Category	3		N=No Y=Yes
13	DACTDAT	Actual Injection Date	DACTDAT	Date/Time	dd/mm/yyyy		
14		Did the subject take oral bridging therapy or any	DBRID	Category	3		N=No Y=Yes
15		started	DBRIDREAS	Text	500		
16	DSRESUME	Did the subject resume the	DSRESUME	Category	3		N=No Y=Yes

	eForm Code: LAREG eForm Title: CAB+RPV LA regimen - Layout						
If the subject received oral bridging the please follow the link below to record	nerapy or any other oral ARV re this in the Antiretroviral Treatn Antiretroviral Treatment Pa						
Discontinuation							
Did the subject discontinue the CAB+PRV LA regimen?	○ No ○ Yes						
Date of discontinuation	DISCONDAT						
Please specify reason for discontinuation				CMRSDISC			
In the event of discontinuation, please Resistance Testing eForm, using the	e complete the resistance test of link below	details on the					
	Resistance Testing						
For Office Use Only							
Data Review Reason  CRREAS	Review Date CRDAT	Notes for Next Review CRNOT					

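### Section 8.7 does not settle whether dosing schedule enters the Cox models, so factors that differ by schedule can be falsely associated with non-adherence

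*Protocol*

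**What the plan says.** The factor analysis closes section 8.7: "Cox regression models will be used to assess the factors associated with virologic failure, with non-adherence and with the discontinuation of CAB+RPV LA regimen". Its candidate factors are set by reference: "All variables described at section 8.3.3 will be assessed". A univariable screen follows: "Variables with univariable P<0.20 will be retained for the multivariable analysis".

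Section 8.3.3 introduces its list with "The study will examine the effect of the following potential confounders and effect modifiers on the risk for outcomes of interest". It then names demographic, virologic, immunologic and clinical variables and comorbidities. "Geographic region" and the regimen start date are on the list; dosing schedule is not.

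The opening paragraph of section 8.7 says: "Study results will be stratified by the regimen used (Q4/Monthly dosing vs Q8/Every 2 month dosing". That sentence stands among rules for descriptive statistics and names no model.

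AIM 2 of section 8.7 measures non-adherence per person in two ways: having missed one or more consecutive injections without oral cover, or having received injections seven or more days late. The denominator is all participants in the analysis. The CAB+RPV LA regimen form in Annex 1 records the dosing type for each scheduled injection (initiation, 1-monthly or 2-monthly), and any change of type with its reason.

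**The concern.** The protocol treats schedule as important enough to stratify results, but leaves it off the list of confounders and effect modifiers that feeds the models.

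For non-adherence the omission matters because of how the outcome is counted. An injection can be late or missed only when one is due, and a participant on monthly dosing has two due dates for every one under 2-monthly dosing. At the same risk per injection, the monthly participant reaches a first event about twice as fast. If schedule is not in the model, any listed factor that differs by schedule (region and start date are plausible examples) can appear to drive non-adherence when it only marks the schedule in use. No other listed variable can adjust this away.

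At stake is the reading of the non-adherence factor results. Section 6.2 gives the impact of non-adherence on failure and resistance as a reason for the study.

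**Working it through.** **Inputs.** From section 8.4: "The study will aim to enroll 1000 PLWH with VL <50 copies/mL", virologic failure 2 to 6%, discontinuation 8 to 16%. From AIM 2: the per-person definition of non-adherence. It is taken here that the Cox model for non-adherence uses that definition. Assumed, because the protocol gives none of it: the schedule mix by region, a late-injection risk of 2 to 5% per injection, and any effect of schedule on failure or discontinuation.

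**The plan's own figures.** Exact 95% half-widths at N = 1000 come to 0.92% (rate 2%) and 1.52% (rate 6%) against a stated 0.9 to 1.5%, and to 1.73% (8%) and 2.32% (16%) against a stated 1.7 to 2.3. Both reproduce, and this point disputes neither. The implied events are 1000 × 0.02 = 20 to 1000 × 0.06 = 60 failures, and 1000 × 0.08 = 80 to 1000 × 0.16 = 160 discontinuations.

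**Non-adherence.** Let q be the risk per injection, equal in both regions and both schedules. The monthly event rate is q under monthly dosing and q/2 under 2-monthly dosing. A region with monthly share m has rate q[m + (1 − m)/2].

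- 60% vs 20%: (0.6 + 0.2)/(0.2 + 0.4) = 0.8/0.6 = 1.33
- 40% vs 20%: (0.4 + 0.3)/(0.2 + 0.4) = 0.7/0.6 = 1.17
- 30% vs 20%: 0.65/0.60 = 1.08
- equal shares: 1.00

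Two independent simulations (N = 1000, 24 months, 200 cohorts per setting, no true region effect) agree:

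| Monthly shares | Region HR, schedule omitted | P<0.05, schedule omitted |
|---|---|---|
| 60% vs 20% | 1.33 to 1.35 | 68 to 94% |
| 40% vs 20% | 1.15 to 1.18 | 19 to 38% |
| 30% vs 30% | no excess | about 5% |

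With schedule as covariate or stratum, the region HR is 0.99 to 1.01 and P<0.05 occurs in 2 to 8%. At 60% vs 20% with schedule omitted, region passes the P<0.20 screen in 89 to 99% of cohorts.

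**Virologic failure and discontinuation.** The count of injections due does not carry over to these outcomes, so a schedule effect h must be assumed. With one schedule's share at a and b in two equal regions, the apparent region HR is [1 + b(h − 1)]/[1 + a(h − 1)]. The chance of P<0.05 follows from √(events × 0.25) × |ln HR|.

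- h = 1, or a = b: HR 1.00, 5%
- h = 1.5, 30/70%: 1.35/1.15 = 1.17; 6.5% at 20 events, 17% at 160
- h = 2, 10/90%: 1.9/1.1 = 1.73; 23% at 20 events, 56% at 60, 93% at 160

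Simulated Cox models (400 per setting) confirm this. For h = 2 and 10/90%, region was flagged in 54% (60 events) and 93% (160 events) with schedule omitted, and in 3.8 to 6.8% with it included. With h = 1, or with a 50/50 split at h = 2, the figures with schedule omitted were 6.0% and 4.8%, within simulation error.

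**Separate models per schedule.** If the stratification sentence means separate fits, an even split would leave 20/2 = 10 to 60/2 = 30 failures per model. No schedule effect would be estimated.

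**The case against.** The stratification sentence opens section 8.7, the factor analysis belongs to that section, and nothing exempts it. Results produced within schedule cannot carry this confounding. The sentence citing section 8.3.3 does not say that only those variables enter, and how a stratifier is carried into a Cox model is often left to the analysis plan. This reading is open, but the protocol does not state it. The two ways of applying it also differ: separate fits split an already small number of failures, while a stratified baseline hazard does not. The protocol has fixed its candidate list, so it should say which is meant.

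A reader might infer that region or start date will be falsely flagged, and for all three outcomes. The documents do not support that. False flagging needs an imbalance of schedule across the factor, and no schedule mix is given. The due-date mechanism applies to non-adherence alone, and nothing shows that schedule affects failure or discontinuation. Section 8.4 also states that no formal hypothesis is tested, so the P<0.05 rates above only gauge size.

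It can also be said that a region with more monthly dosing truly has more late injections, so the unadjusted association is real. That stands: adjustment answers a different question, namely the association given schedule. Section 8.9 does acknowledge confounding by indication, but a general caution does not tell the analyst what to fit.

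**Conclusion.** The point holds as a gap between two parts of section 8.7. Schedule is the protocol's stratifier and is recorded for each injection, but it is missing from the list that feeds the models, and its role in them is not stated.

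For non-adherence a distortion follows from the outcome definition whenever schedule differs across a factor and the risk per injection is similar between schedules. Its size depends on the assumed mix: HR about 1.33 at 60% vs 20% monthly, about 1.17 at 40% vs 20%, none if balanced. For virologic failure and discontinuation the risk is conditional on a schedule effect that the document does not show, and it is small with few events or moderate imbalance. One model containing schedule is the better choice on either reading of the stratification sentence, so the text should be amended.

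**What to change.** - Add dosing schedule (monthly or every 2 months) to section 8.3.3.
- State in section 8.7 that each outcome has one Cox model with common coefficients for the other factors, not a separate model per schedule. The model includes schedule whatever its univariable P value, as a baseline-hazard stratum, or as a covariate where its own effect is wanted.
- Derive schedule from the dosing type already recorded in Annex 1, updated over time when it changes. Fixing it at the first injection would misclassify participants who change schedule.
- Give a rule for participants who stop while their rows are still coded as initiation, since they otherwise have no schedule.

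The cost is one model term and time-updated data preparation; the dosing type is already collected. A stratum gives no estimate for schedule itself, hence the covariate option. The factor results become associations given schedule; the unadjusted univariable results can still be shown beside them.

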#### 6.2. Rationale

Adherence to scheduled dosing visits to help maintain viral suppression and reduce the risk of viral rebound and potential development of resistance with missed doses is critical for long term maintenance of viral suppression with the regimen. Impact of non-adherence on virologic failure and emergence of resistance need to be assessed in real world clinical setting. Discontinuations for other reasons such as individual choice, drug interactions and pregnancy will also be captured. The gathering of this real world evidence would further demonstrate the value of this regimen.

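### No planned analysis relates missed or late injections to virologic failure or resistance, and the failure Cox model screens about 24 candidates at P<0.20 on an expected 20 to 60 failures

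*Protocol*

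**What the plan says.** Section 6.2 (Rationale) sets the question: "Impact of non-adherence on virologic failure and emergence of resistance need to be assessed in real world clinical setting".

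Section 8.7 deals with adherence in two places. Under Aim 2, missed injections without oral cover and injections seven or more days late are summarised by counts, proportions with confidence intervals, and medians with quartiles. Under the assessment of factors, non-adherence is the dependent variable of its own Cox model, alongside Cox models for virologic failure and for discontinuation. A logistic model is planned for resistance among failures, on condition that there are enough events.

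The covariate rule for these models is fixed in the same place: "All variables described at section 8.3.3 will be assessed", then "Variables with univariable P<0.20 will be retained for the multivariable analysis". Continuous variables are entered as continuous or as terciles, whichever has the lower AIC in the univariable model, and some variables are collapsed to two classes. The stated purpose is to "identify factors that probably modified the effect of the study treatment".

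On size, Section 8.4 says "The study will aim to enroll 1000 PLWH with VL <50 copies/mL" and continues: "If the virological failure rate is ranging from 2 to 6" per cent, then "the number of participants to be tested for genotypic resistance will range from 20 to 60 individuals".

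Annex 1 (CAB+RPV LA regimen eForm) records the scheduled date, whether the injection was given, the "Actual Injection Date", and whether oral bridging or another oral regimen was taken.

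**The concern.** The exposure that the rationale singles out is missing from every model that could relate it to failure or resistance. If the plan is followed as written, the report will say how often injections were missed or late and how often failure occurred, but not whether the two go together.

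The models that are planned for failure use a rule poorly matched to the expected data. A long list, a permissive univariable screen and data-chosen coding are applied to a few dozen events at most. Chance associations then enter the multivariable model easily, real ones are estimated imprecisely, and those that survive selection tend to be exaggerated. The results are meant for healthcare providers and regulators (Section 11.2).

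**Working it through.** **1. Does any analysis link adherence to failure or resistance?** Reading Section 8.7 through:
- Aim 2: describes missed and late injections; no failure or resistance outcome.
- Aim 3: estimates failure and resistance; adherence does not appear.
- Aim 4: regimens and viral load after the switch; adherence does not appear.
- Factor assessment: non-adherence is an outcome; candidates come from Section 8.3.3.
- Section 8.3.3: demographics, and virologic, immunologic and clinical variables at initiation, with comorbidities. No missed-injection or late-injection variable is listed.

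None does.

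**2. The plan's own figure.** 1000 × 0.02 = 20 and 1000 × 0.06 = 60 failures, as Section 8.4 states. Its Clopper-Pearson limits also reproduce: 1.2% to 3.1% at 2%, and 4.6% to 7.7% at 6%.

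**3. Number of candidates K in Section 8.3.3.** 8 demographic + 1 baseline viral load + 2 CD4 (count, nadir) + 7 clinical + 6 comorbidities = 24, taking BMI, height and weight as one item and concurrent medication as one. Height and weight separate: 26. Baseline viral load has one permitted category and is constant as categorised; dropping it gives 23 to 25. With the 27 medicines counted singly: 24 − 1 + 27 = 50. Ethnicity, region, route and subtype are multi-category, so model terms exceed K.

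**4. Failures per candidate (events / K).** K = 24: 20/24 = 0.8 and 60/24 = 2.5. K = 50: 0.4 and 1.2.

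**5. Null variables expected to pass P<0.20 (0.20 × K).** K = 23: 4.6; K = 25: 5.0 (binomial 95% range 1 to 9); K = 26: 5.2; K = 50: 10. Simulating the screen with 1000 participants and 25 independent null variables gave 5.2 retained at 20 failures and 4.9 at 60.

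**6. Precision of one hazard ratio.** For a binary factor of prevalence q (assumed), unadjusted, SE(log HR) ≈ 1/√(events × q(1−q)). A factor passes P<0.20 if |log HR| > 1.28 × SE.

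| Failures | q | SE | 95% CI: HR ÷ and × | HR needed to pass | Chance a true HR of 2 passes |
|---|---|---|---|---|---|
| 20 | 50% | 0.447 | 2.4 | 1.8 | 61% |
| 20 | 20% | 0.559 | 3.0 | 2.05 | 48% |
| 60 | 50% | 0.258 | 1.7 | 1.4 | 92% |
| 60 | 20% | 0.323 | 1.9 | 1.5 | 81% |

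At 20 failures and 20% prevalence, a true doubling of the hazard is lost about half the time, and when retained its univariable estimate is at least about 2.05. For a null factor of 5% prevalence, the chance that none of 20 failures is exposed is 0.95^20 = 36%, in which case the hazard ratio has no finite estimate. Joint adjustment for several retained variables can only widen these intervals further.

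**7. Other models.** Discontinuation: 8% to 16% of 1000 = 80 to 160 events, or 3.3 to 6.7 per candidate at K = 24. Resistance: 50% of 20 to 60 = 10 to 30 events, with an event-count condition attached. Non-adherence: no event count is stated.

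**The case against.** The best defence is that the factor analysis is exploratory. Section 8.4 disclaims any formal hypothesis, Section 8.9 asks for cautious reading, and the text says all Section 8.3.3 variables will be assessed, not only those, so an analysis plan not shown could add adherence. That is fair as far as it goes. But the protocol itself names the source of covariates and the selection rule, and both fall short of its own rationale.

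Several stronger readings are tempting and are not supported.
- **That the reported factors would be mostly noise.** This depends on how many true factors exist, which the protocol does not say. At the screen, with true factors of HR 2, noise is 60% to 83% of retained variables if 2 or 3 of 25 are real, but about 32% to 47% if 8 are. In simulated final models with three true factors (HR 2 per SD), about one false factor appeared against about 2.5 true ones at 20 failures, and about one against three at 60.
- **That the chance of at least one false factor measures the harm of the screen.** With 25 null variables it is about 67% after screening, but testing 25 independent nulls at 0.05 already gives 1 − 0.95^25 = 72%. The figure reflects the number of tests, not the screen or the scarcity of failures.
- **That all the risk-factor models are this thin.** The 20 to 60 events belong to the failure model only.
- **That dosing interval is ignored.** Section 8.7 stratifies results by monthly and two-monthly dosing.
- **That the study cannot answer the adherence question.** The data are collected; what is missing is the planned analysis.
- **That effect modification is a planned analysis.** With no comparator it could not be estimated, but the section heading and following sentences speak of association, so this is a matter of wording.

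**Conclusion.** The point stands in two parts. First, the protocol says the effect of non-adherence on failure and resistance must be assessed and then plans no analysis of it. This rests on the text alone.

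Second, the failure Cox model has a selection rule ill-suited to its expected size: roughly 0.8 to 2.5 failures per candidate, about 5 null variables expected through the screen if 25 were null, and imprecise, selection-inflated hazard ratios at the low end. The condition on the number of events protects only the resistance model. This part assumes the protocol's 2% to 6% failure rate with full enrolment, the candidate count above, and, for step 6, assumed prevalences. It does not establish what share of the finally reported factors would be false.

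Both should be corrected. Neither affects the descriptive estimates of failure, discontinuation or resistance.

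**What to change.** 1. In the factor assessment of Section 8.7, add non-adherence as a time-updated covariate in the failure Cox model: a missed injection without oral cover, or an injection seven or more days late, counted only from when it occurs and before the failure date. An ever/never variable would bring immortal-time bias. Combine the two into one term when failures are few: at 20 failures, a rule of thumb of one parameter per 10 failures leaves room for only two. Dosing interval can stay with the existing stratification.
2. Tabulate prior adherence by resistance status among participants with failure.
3. For the failure model, replace the P<0.20 screen and data-driven cut-points with a short prespecified covariate list that includes the adherence term and is sized to the observed number of failures, with penalised estimation (for example Firth) when events are few. At the least, extend the event-count condition to this model.
4. Wording only: describe the aim as finding factors associated with the outcome.

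The cost is protocol text and programming. Scheduled and actual injection dates and oral cover are already on the case report form. The downside is fewer factors in the multivariable failure model.
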